#### 7.2 SCREENING VISITS

#### PRELIMINARY SCREENING

A research coordinator will conduct preliminary screening prior to contacting patient.

#### SCREENING VISIT

Upon reaching out to patient, the coordinator will confirm enrollment eligibility with the patient prior to consenting.

#### 7.3 VISIT 1

Visit 1 is performed by the coordinator. It consists of the following forms:

- Phone consent
- Enrollment Eligibility Form
- ER Admission Data Form
- Demographics and Subject History Form
- Participant Contact Form
- Medications Form
- CPAP and WatchPAT Assignment Form
- PROMIS questionnaire Form
- Randomization Form
- Respiratory Questionnaire Form
- 1. Once the Mount Sinai team has randomized patient, we will email [contact] with demographics and equipment ordered.
- 2. Community surgical will call patient to confirm address and information, they will then initialize the WatchPAT.
- 3. The pin used will be the DOB in the following format: MMDD
- 4. The pin will be written on the WatchPAT box as well
- 5. Community surgical will then deliver the equipment box to the patient. Patient will receive documents to sign via docusign.

- 6. Once delivery has been made, community surgical will notify PI
- 7. Community surgical will register patient on encoreanywhere once patient has been registered it will take approximately 24 hours before we are able to see the patient on our end

#### 7.4 VISIT 2 (EQUIPMENT SET UP CALL)

Visit 2 is done by the sleep technicians. It consists of the following forms:

- CPAP Set Up Form
- WatchPAT and POX Set Up Form

#### 7.5 6-12 HOUR CHECKINS (UP UNTIL 72 HOURS)

The subsequent check-ins are done by the coordinator. They consist of the following forms:

- Follow-up Questionnaire
- Respiratory Questionnaire Form
- CPAP Adherence Form
- CPAP Use Form

#### 7.6 DAILY CHECKINS (DAYS 4-7)

After 72 hours, check-ins occur daily. For patients on CPAP, the forms to be filled out are:

- Follow-up Questionnaire
- Respiratory Questionnaire Form
- CPAP Adherence Form
- CPAP Use Form

For patients not on CPAP, the forms to be filled out are:

- Follow-up Questionnaire
- Respiratory Questionnaire Form

#### 7.7 DAILY CHECKINS (DAYS 8-14, 28)

After 7 days, check-ins continue to occur daily. For patients on CPAP, the forms to be filled out are:

- Respiratory Questionnaire Form
- Interval Assessment Form
- Investigator Statement Form (Day 28)

#### 8 – WITHDRAWLS AND DROP-OUTS

#### 8.1 REFUSAL OF PARTICIPATION

A record will be kept of all participants who are ineligible, or approached but are not interested in participation in the study prior to the signing the ICF. This is to prevent double calling patients. The MRN and reason for ineligibility/disinterest will be logged in Ripple. We will let the patients we call know their MRN will be stored in Ripple. This data will be deleted when the study is over.

#### 8.2 WITHDRAWALS

Participants whose participation in the study is terminated prematurely (before final participant completes their 28-day endpoint visit) at their own discretion or that of the investigator are considered withdrawals. The withdrawal request can be made during a phone contact. When possible, willing participants will have follow-up data collected, including electronic medical record data.

#### REASONS FOR WITHDRAWAL

Participants are free to withdraw from the study at any time. The various reasons for withdrawal may include:

- o Experiencing an AE;
- Dissatisfaction with treatment;
- o Significant concurrent illness;
- Loss of interest in the study;
- o Relocation.

Participants may also be withdrawn from the study by the investigators, for protocol non-compliance or other reasons at the discretion of the site PI. All withdrawals should be reported following the procedures below.

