- 8) All patients will be contacted every 6-12 hours to complete follow up assessments. These follow ups will be done via a phone call. If the timing of these follow ups fall between 10pm-6am, the follow up will be deferred until after 6am. After 72 hours, all patients will then be contacted daily until day 14 from randomization. After day 14, research staff will continue to monitor the medical charts for any visits to the hospital. One last contact will be made on day 28.
- 9) After 72 hours, patients will be asked to discontinue using the CPAP and pulse oximeter. If patients wish to continue to use the CPAP, they may do so for up to 7 days from time of randomization.
- 10) The research staff will continue to call all patients daily (after the 72 hour mark) to assess symptoms.
- 11) The patients can also choose to monitor their oxygen saturation beyond the 72 hours of treatment.
- 12) CPAP download is available continuously however we will download data on usage, pressure, leak daily and make adjustments to the mask or CPAP pressure as needed for patient comfort. For patients experiencing significant trouble tolerating high pressure, we will decrease CPAP from 8-10 cm to a fixed CPAP of 5 cm for 2-4 hours after which we will raise it back to 8-10cm for the

- duration of the study. If the patient is not able to tolerate the pressure again, we will reduce it back to 5cm of water pressure for several hours before increasing the pressure. This will be continued until the patient withdraws or 72 hours are completed, whichever occurs first.
- 13) Patients will be asked to track their own oxygen saturation using the provided pulse oximeter and report it when we contact them for the 6-12 hour follow up calls/surveys.
- 14) The sleep apnea test will provide continuous oxygen and breathing data for a period of 12 hours during the 72 hours and will also provide information on oxygen saturation while the patient is asleep.

The outline of the forms that correspond to the study visits can be found in the Appendix, Figure 1. All of these forms are subsequently included in the following appendicies.

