#### PROCEDURES FOR WITHDRAWAL

Once it has been established that a participant is going to be withdrawn from the study, the study coordinator should complete the End of Study CRF. If the participant has been randomized, the study coordinator should also complete the Treatment Stop CRF.

Study Stop Resulting from Withdrawal

Once withdrawal is established the study coordinator fills out the End of Study CRF by recording:

- That the participant did not complete the study per protocol;
- o The last study visit the participant completed;
- The date participation stopped (the day withdrawal was established); The primary reason cited for ceasing participation;

The End of Study CRF must be completed in Slice within 24 hours of withdrawal. This will allow the DCC to begin the data archival process.

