#### 10.5 DISCONTINUATION

#### DISCONTINUATION – TREATMENT STOP/DISCONTINUATION

Participants may require additional/alternative therapies that may or may not be exclusionary criteria and are designed to minimize the potential risks to participant's safety which can result in discontinuation of the study treatment. Discontinuation can be observed during either routine interim follow-up phone calls or visits, or as a result of study contact by the participant or the participant's physician. If the participant is deemed a 'discontinuation – treatment stop', the Treatment Stop CRF must be completed, arrangements for the return of the concentrator must be made, and the participant should still be followed-up per protocol, despite no longer receiving the study intervention, if agreed. Discontinuation – treatment stop in PAP-COVID are defined as follows:

• The participant's physician has identified a change in signs or symptoms that in his/her opinion are related to ongoing symptoms of COVID-19 and therefore warrant alternative treatment, such as permanent supplemental oxygen

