Proportion of patients with Negative outcome	Control	0.25	0.30	0.35	0.4	0.45	0.5
	СРАР	0.09	0.12	0.16	0.20	0.25	0.29
	Relative reduction in CPAP arm (%)	64	60	54	50	44	42

Randomization Design and Procedure

Patients will be randomized using a 1:1 allocation to CPAP versus control group. The randomization will be stratified by BMI ($\geq=30$ and ≤30), gender and age (≤60 , $\geq=60$). A random permuted block design will be employed, with random blocks of size 2 and 4.

Data Monitoring and Analysis

Primary Efficacy Analysis

The primary efficacy endpoint is the proportion of patients with a negative composite endpoint within 14 days of randomization and will be compared between CPAP and control groups. The null hypothesis is that the proportion of patients with a negative outcome will be the same between patients randomized to CPAP versus control arm. This hypothesis will be tested using a two-sided Fisher's exact test at 0.05 alpha level. The primary analysis will be conducted according to the intention-to-treat principle.

Early stopping rule: If three deaths are observed in the CPAP group, enrollment will be halted pending DSMB review and recommendations. As of April 03, the death rate for COVID-19 positive patients in NYC was 2.99% [95% Clopper Pearson CI= 2.986, 2.997]. The rate is expected to be lower for our patient population. As such, 3 deaths among 100 patients will indicate a proportion of 3% [95% CI: 2.57%, 3.78%].

Analyses of Secondary Endpoints

Safety

Safety analyses will be conducted according to randomization assignment and treatment actually received. Adverse event rates will be calculated as the ratio of the total number of events over 14 days divided by total patient-days at risk for the specific event from randomization. A Poisson model with robust variance estimation will be used to compare SAEs between CPAP and control patients.

Time-to-events outcomes

Time from randomization to event outcomes (Hospitalization or ED visit, ICU admission, intubation and mechanical ventilation) within 14 days of randomization will be compared between randomization groups using a log-rank test or Gray's test in the presence of competing risk of death. In addition, survival at days 14 and 28 post-randomization will be described by Kaplan-Meier curves and a log-rank test will be used to compare survival between the two groups.

Respiratory Function

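### Investigators may withdraw randomized patients from the study for non-compliance, which risks avoidable loss of contact-based outcomes, probably more often in the CPAP arm

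*Protocol*

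**What the plan says.** **Grounds for withdrawal.** Protocol section 8.2, Reasons for Withdrawal: "Participants may also be withdrawn from the study by the investigators, for protocol non-compliance or other reasons at the discretion of the site PI". Section 8.2 defines withdrawal as premature end of study participation; patients who leave "at their own discretion or that of the investigator are considered withdrawals".

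**What follows.** Under Procedures for Withdrawal, the End of Study CRF is due within 24 hours. The stated purpose is: "This will allow the DCC to begin the data archival process". The same section adds: "If the participant has been randomized, the study coordinator should also complete the Treatment Stop CRF". Later data collection is conditional: "When possible, willing participants will have follow-up data collected, including electronic medical record data".

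**Pressure intolerance.** Section 7.1, item 12, describes a repeated cycle of pressure adjustment and closes: "This will be continued until the patient withdraws or 72 hours are completed, whichever occurs first". It names no state in which the patient is off CPAP but still in the study.

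**Treatment stop.** Section 10.5 does describe that state: "the participant should still be followed-up per protocol, despite no longer receiving the study intervention, if agreed". Its visible definition is a change in signs or symptoms identified by the patient's physician. It does not name intolerance or non-compliance.

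**Analysis.** The SAP, Primary Efficacy Analysis: "The primary analysis will be conducted according to the intention-to-treat principle". SAP, Sample Size and Power, expects the primary outcome on all patients, makes no allowance for drop-out, and scores any missing primary outcome as a failure.

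**The concern.** Under intention to treat, what happens to patients who stop or never properly use the treatment is part of the answer, so their outcomes should be observed. A rule that ends study participation for non-compliance works against that aim. The decision rests with staff who know the allocation, and the most demanding thing to comply with, near-continuous CPAP for 72 hours, exists in one arm only.

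Three things are at stake.

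- **Primary outcome.** Two of its four components are saturation events in the first 72 hours. Section 7.1, item 13, has the patient report oximeter readings at the follow-up calls, and WatchPAT covers only 12 hours. If the calls stop, most of this information stops. The SAP does not say how to score a patient whose hospital status is known but whose saturation is not.
- **Secondary outcomes.** Symptom scores come from calls. Household conversions would not reliably appear in the participant's own chart.
- **Safety.** The failure rule covers only the primary outcome. Adverse-event rates are events per patient-day at risk over 14 days, with no rule for follow-up cut short by withdrawal. The patients lost could be those who tolerated the device worst.

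**Working it through.** **Inputs from the SAP.** 100 patients per arm; two-sided Fisher's exact test at 0.05; six pairs of control and CPAP failure rates; no drop-out allowance; missing primary outcome = failure.

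**Input not in the documents (assumption).** w, the share of CPAP patients withdrawn for non-compliance; 5% and 10% are shown. No control patient is withdrawn, and the remaining CPAP patients keep the SAP's CPAP rate.

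**Step 1: reproduce the SAP table.** Exact power, by full enumeration of both binomials:

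| Control | CPAP | Power |
|---|---|---|
| 0.25 | 0.09 | 83.0% |
| 0.30 | 0.12 | 85.4% |
| 0.35 | 0.16 | 84.3% |
| 0.40 | 0.20 | 84.5% |
| 0.45 | 0.25 | 80.9% |
| 0.50 | 0.29 | 83.3% |

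All exceed 80%, as the SAP states. None of its figures is wrong on this point.

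**Step 2: two fates for the same patients.** Let pc and pt be the control and CPAP failure rates.

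- Withdrawn, nothing recovered, scored as failures: CPAP rate = (1 − w)·pt + w.
- Followed, with control-arm risk because they are off treatment: CPAP rate = (1 − w)·pt + w·pc.

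For 0.35 versus 0.16:

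- w = 5%, withdrawn: 0.95 × 0.16 + 0.05 = 0.202
- w = 5%, followed: 0.152 + 0.05 × 0.35 = 0.1695
- w = 10%, withdrawn: 0.90 × 0.16 + 0.10 = 0.244
- w = 10%, followed: 0.144 + 0.10 × 0.35 = 0.179

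**Step 3: power for a significant result in favour of CPAP.**

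| Scenario | w | Withdrawn, scored as failure | Followed, control-arm risk |
|---|---|---|---|
| 0.25 vs 0.09 | 5% | 47.2% | 77.7% |
| | 10% | 17.2% | 71.6% |
| 0.35 vs 0.16 | 5% | 59.4% | 79.6% |
| | 10% | 31.9% | 74.2% |
| 0.50 vs 0.29 | 5% | 66.8% | 79.0% |
| | 10% | 46.7% | 74.2% |

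The cost of losing follow-up is the difference between the last two columns. At 0.35 versus 0.16 it is 79.6 − 59.4 = 20.2 points at w = 5% and 74.2 − 31.9 = 42.3 points at w = 10%. The fall from 84.3% to the last column is the effect of not using CPAP, which better follow-up cannot restore.

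**Step 4: safety.** A patient withdrawn on day 3 leaves 14 − 3 = 11 days of the adverse-event window without scheduled contact. The denominator shortens too, so the rate is biased only if withdrawal is related to the risk of an event. With poor tolerance as a route to withdrawal, that is possible.

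**The case against.** The strongest case against the point is that the plan already limits the damage, and much of that case stands.

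- **Deaths and admissions are largely recoverable.** Section 6.1 includes review of vital status and hospitalizations in the consent procedure, with requests for outside records. Section 8.2 mentions electronic records after withdrawal, and section 10.8 has a medical release signed at enrolment. A patient withdrawn by the investigator has not revoked that consent. A reader might infer that deaths will drop out of the three-death trigger. That is a worst case, chiefly for events outside the health system, since outside records are sought when a hospitalization is reported.
- **Intention to treat is not formally breached.** A reader might infer that withdrawn patients leave the primary analysis. They do not, because the failure rule keeps them in.
- **Controls can be non-compliant too.** Both arms have an oximeter, a WatchPAT night and frequent calls. It would be wrong to say that control patients have no equivalent exposure to withdrawal; CPAP is an additional demand.
- **Section 10.5 is not directly contradicted.** Its visible definition does not mention intolerance, I could not see all of the text that follows it, and the withdrawal in section 7.1, item 12, may simply mean stopping CPAP. This is a gap and an ambiguity.
- **Part of any power loss is ordinary non-adherence.** This is why the comparison above is with the same patients followed, not with w = 0.

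What remains is that conditional follow-up and record review do not replace contact for self-reported saturation, symptoms, non-hospital adverse events and household conversions.

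**Conclusion.** The point holds as an avoidable weakness in follow-up. As written, section 8.2 lets unblinded investigators end study participation for non-compliance, starts closing the record within 24 hours, and leaves later data collection conditional. Losses are likely to be greater in the CPAP arm. In the primary analysis, the consequence is imputed instead of observed outcomes, with a bias against CPAP. In the safety analysis, it is possibly informative loss of follow-up for which the SAP has no rule.

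At 35% versus 16%, the illustration gives 59% against 80% power at w = 5%, and 32% against 74% at w = 10%. These figures assume CPAP-only withdrawal, no recovered outcome, and control-arm risk in the patients who are followed. The documents give no withdrawal rate, so the figures show sensitivity and are not a forecast. Record review, or some withdrawals among controls, would narrow the gap. The documents do not support the stronger conclusions that intention to treat is broken, that deaths will go uncounted, or that section 10.5 is contradicted outright.

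**What to change.** 1. In section 8.2, remove protocol non-compliance as a ground for investigator withdrawal from the study. Let follow-up end only at withdrawal of consent to follow-up, death, day 28, or loss to follow-up handled under section 8.3.
2. State that patients who do not use or do not tolerate CPAP remain in all scheduled calls and in chart review to day 28.
3. Make electronic-record follow-up after withdrawal a requirement wherever consent allows it.
4. Reconcile section 7.1 item 12, section 8.2 (grounds and procedures), section 8.3 and section 10.5, so that stopping CPAP is recorded separately from leaving the study and the End of Study CRF has one consistent trigger, including for drop-outs. This should leave every pressure, device-return and CPAP-stopping rule as it is.

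The cost is protocol wording and a few more calls. Calls to day 14, chart monitoring and the day-28 contact are already planned for every patient.

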#### PROCEDURES FOR WITHDRAWAL

Once it has been established that a participant is going to be withdrawn from the study, the study coordinator should complete the End of Study CRF. If the participant has been randomized, the study coordinator should also complete the Treatment Stop CRF.

Study Stop Resulting from Withdrawal

Once withdrawal is established the study coordinator fills out the End of Study CRF by recording:

- That the participant did not complete the study per protocol;
- o The last study visit the participant completed;
- The date participation stopped (the day withdrawal was established); The primary reason cited for ceasing participation;

The End of Study CRF must be completed in Slice within 24 hours of withdrawal. This will allow the DCC to begin the data archival process.

#### 8.3 DROP-OUTS

Participants who drop out will be distinguished from those who withdraw based on whether they actively withdraw versus passively dropped out by not responding to phone interviews.

#### PROCEDURES FOR DROP-OUTS

Participants who do not answer or respond to phone calls will be considered possible drop-outs. Following a missed visit, the study coordinator must:

- o Immediately place a call to the participant in an attempt to re-establish contact and leave a voice message if possible detailing the importance of contacting study staff in order to gather critical data, whether or not they intend to continue participation.
- o Query the Mount Sinai Expired list, frequently.
- O Continue to call twice a day for 7 days until you hear from patient. If patient misses 2-3 consecutive calls, check the emergency contact.
- Once the participant has not responded and the emergency contact is unavailable, the PI should be notified. The End of Study form may be filled out given the situation.

#### 8.4 VISIT WINDOWS AND MISSED VISITS

#### **VISIT WINDOWS**

Check-ins should occur based on the "schedule" form.

#### MINIMIZING MISSED VISITS

To minimize the occurrence of missed appointments, the participant should be provided with the following when appropriate:

- Visit Schedule of in-window visits generated and provided at the baseline visit;
- Text reminders to patients to fill out forms

#### 9 – RANDOMIZATION

#### 9.1 ELIGIBILITY FOR RANDOMIZATION

Only participants who have successfully completed the entire screening process will be eligible for randomization. The following will be assessed to confirm eligibility:

 The inclusion and exclusion criteria will be reviewed, checked, and verified by completing the Screening and Eligibility CRF during the screening and baseline visit prior to randomization.

The PI and study coordinators will be the only people who has authorization to access the randomization database. The study coordinator must complete the Screening and Eligibility CRF in RedCAP to receive the computer-generated randomization code. The randomization code will not be assigned until all the questions have been answered and automatically crosschecked in the system with previously entered data to confirm eligibility. The randomization process is an administrative task that occurs after all the screening and baseline data have been collected and entered into RedCAP. The study coordinator may randomize the subject at the end of the baseline visit with the participant present or within 12 hours of the baseline visit.

#### 9.2 RANDOMIZATION PROCEDURES

#### ELECTRONIC RANDOMIZATION

The PI and Research Manager will be responsible for randomization. Once patient has been deemed eligible and coordinator has entered in the appropriate documents, the PI will review with the research manager and sign off. An automatic electronic randomization process has been built in to the redcap database.

#### 10 – PROTOCOL DEVIATIONS AND ADVERSE EVENTS

#### 10.1 PROTOCOL DEVIATIONS

**Deviations** are variances from the IRB (and sponsor when one exists) approved protocol/protocol related materials that have not been pre-approved and 1) imposed no increase in risk to the participant and 2) did not result in a negative consequence and is not anticipated to result in a negative consequence in the future.

**Violations** are variances from the IRB (and sponsor when one exists) approved protocol/protocol related materials that have not been pre-approved and 1) imposed an increase in risk to the participant and/or 2) resulted in a negative consequence or is anticipated to result in a negative consequence in the future.

